AE	Adverse Event/Adverse Experience
BID	Twice a day
CDC	Centers for Disease Control and Prevention
CDM	Center for Data Management
CI	Confidence Interval
CFR	Code of Federal Regulations
CPM	Clinical Project Manager
CRF	Case Report Form
CROMS	Clinical Research Operations and Management Support
CT	Chlamydia Trachomatis
DHHS	Department of Health and Human Services
DM plan	Data Management Plan
DMID	Division of Microbiology and Infectious Diseases
DSMB	Data and Safety Monitoring Board
EMR	Electronic Medical Record
FDA	Food and Drug Administration
GC	Neisseria Gonorrhoeae
GCP	Good Clinical Practice
gm	Gram
HIV	Human Immunodeficiency Virus
IC	Informed Consent
ICF	Informed Consent Form
ICH	International Conference on Harmonisation
ICMJE	International Committee of Medical Journal Editors
IDE	Investigational Device Exemption
IEC	Independent or Institutional Ethics Committee
IND	Investigational New Drug Application
IRB	Institutional Review Board
LA	Los Angeles
LACDPH	Los Angeles County Department of Public Health
MedDRA®	Medical Dictionary for Regulatory Activities
mg	Milligrams
NAAT	Nucleic Acid Amplification Test
NGU	Nongonococcal Urethritis
NIAID	National Institute of Allergy and Infectious Diseases
NIH	National Institutes of Health
OHRP	Office for Human Research Protections
OmpA	Major Outer Membrane Protein
PCR	Polymerase Chain Reaction
PD	Protocol Deviation
PI	Principal Investigator

PO	By mouth
PS	Protocol Specialist
QA	Quality Assurance
QC	Quality Control
SAE	Serious Adverse Event/Serious Adverse Experience
SAS	Statistical Analysis Software
SC	Study Coordinator
SI	Site Investigator
SOP	Standard Operating Procedure
STD	Sexually Transmitted Disease
STI	Sexually Transmitted Infection
STI CTG	Sexually Transmitted Infection Clinical Trials Group
UAB	University of Alabama at Birmingham
US	United States
USC	University of Southern California
WHO	World Health Organization
YCF	Youth Correctional Facility

PROTOCOL SUMMARY

Title:	Evaluation of Treatment Failure and Associated Predictors Following Azithromycin Treatment for Urogenital Chlamydial Infection in Males in Youth Correctional Facilities (YCFs)
Phase:	Not applicable
Population:	Up to 446 males ages 12-21 in good health identified as chlamydia-infected through screening who are residing in long-term gender-segregated YCFs in Los Angeles County.
Number of Sites:	1 site which is comprised of the Los Angeles County Department of Public Health and 15 YCFs located within Los Angeles County: Los Padrinos Juvenile Hall; Central Juvenile Hall; Barry J. Nidorf Juvenile Hall; Dorothy Kirby Center; Camp Afflerbaugh; Camp David Gonzales; Camp Joseph Paige; Camp Glenn Rockey; Camp Gregory Jarvis; Camp Ronald McNair; Camp Ellison Onizuka; Camp Judith Resnik; Camp Francis J. Scobee; Camp Michael Smith; and Camp Kilpatrick
Study Duration:	4 years
Subject Participation Duration:	28 days
Description of Agent or Intervention:	Azithromycin (1 gm PO single dose) for the treatment of urogenital chlamydia
Objectives:	
Primary: Assess the microbiological efficacy of azithromycin in uncomplicated Chlamydia trachomatis infection in males with versus without urethral symptoms in YCFs; in essence, this study will assess the frequency of chlamydia treatment failure to azithromycin at the Day 28 follow-up visit (Visit 2) in males with urethral symptoms compared to males without urethral symptoms.
 
Secondary: Evaluate the association of laboratory findings (enrollment chlamydia load and OmpA genotype) and other participant characteristics (demographics, sexual behaviors, etc.) to chlamydia treatment failure in males after azithromycin treatment.

Estimated Time to Complete Enrollment:	3.3 years

Description of Study Design:

2 BACKGROUND INFORMATION AND SCIENTIFIC RATIONALE

2.1 Background Information

Chlamydia trachomatis infection (chlamydia) is a public health concern. The World Health Organization (WHO) estimates there are >105 million new cases of chlamydia annually.¹ In the U.S. alone, approximately 3 million new cases of chlamydia are reported yearly, and the costs associated with their management and complications exceed \$2 billion.² Chlamydia can spread to the upper urogenital tract, which can cause significant morbidity. Chlamydia is a leading preventable cause of infertility worldwide. Inflammation associated with urogenital chlamydia can also increase the risk of acquisition and transmission of human immunodeficiency virus (HIV). In many populations, the majority of chlamydia-infected individuals are asymptomatic,³ and unless the infection is detected through chlamydial testing (screening), their infection may be missed and transmitted to others or lead to complications. Chlamydia testing can now be performed on non-invasively collected specimens (e.g., urine) using sensitive and specific nucleic acid amplification tests (NAATs), which should facilitate screening in nontraditional clinical settings (e.g., correctional facilities).

The Centers of Disease Control and Prevention (CDC) recommends either azithromycin 1 gram (gm) by mouth (PO) once or doxycycline 100 milligrams (mg) PO twice daily (BID) for 7 days as co-equal therapies for uncomplicated chlamydia.⁴ This recommendation is supported by a meta-analysis by Lau et al. of 12 randomized clinical trials of azithromycin versus doxycycline for urogenital chlamydial infections, in which microbial cure rates (based on chlamydia culture in 9 of the 12 trials) were 97% and 98%, respectively, and after pooling the data, the efficacy difference for microbial cure between the 2 drugs was not statistically significant.⁵ However, most efficacy studies of therapy for chlamydia relied on measuring outcome (i.e., test of cure) using diagnostic tests with lower sensitivity than NAATs (e.g., culture), and therefore may have underestimated treatment failure. Other limitations of prior chlamydia treatment studies included inability to limit repeat sexual exposure and nonadherence with the multi-dose doxycycline regimen. The possibility of higher treatment failure rates was supported by: 1) high observed chlamydia recurrence rates⁶⁻⁹ (around 20% a few months post-therapy), which may represent treatment failure or repeat acquisition of chlamydia; 2) an *in vitro* study reporting differences in chlamydia eradication based on whether chlamydia is in an acute or persistent state, with doxycycline more effective against the former and azithromycin against the latter;¹⁰ and 3) a study utilizing chlamydia NAATs demonstrating repeat chlamydia rates of 8% at 10-18 weeks following azithromycin treatment in women who denied interval sexual activity.¹¹

Chlamydia prevalence is high in male and female adolescents,¹² especially those entering YCFs, where it has been reported in about 3-9% of males and 12-25% of females.¹³⁻¹⁵ Long-term gender-segregated YCFs (usual continuous stay >4 weeks) are an ideal setting to study the true efficacy of chlamydia treatment because: 1) this population has a high chlamydia prevalence; 2) recurrent or new chlamydia can be excluded (due to the institutionalized setting without the ability to leave the facility unsupervised and that all participants residing in the facility

can be tested and treated at study initiation, minimizing exposure or re-exposure to other infected persons; see Section 4 for more detailed information on furloughs); and 3) nonadherence to chlamydia treatment can be limited as study medications can be given as directly observed therapy. Genotyping of the *C. trachomatis* major outer membrane protein (OmpA) is an additional tool that can be useful in confirming treatment failure. In the clinical setting of a gender-segregated YCF and in the absence of exposure to the original infecting partner, the finding of identical *ompA* sequences of the chlamydial strains from the screening visit and the repeat chlamydia-positive follow-up visit essentially confirms treatment failure (it would be very unlikely that the participant would be exposed to a new partner with the identical *ompA* sequence and there is expected to be no variation in the sequence of a participant's initial and follow-up *C. trachomatis* isolate with treatment failure).

Determining the true efficacy of chlamydia treatment regimens and whether a repeat positive chlamydia test post-therapy represents chlamydia treatment failure or recurrence is a public health priority. Considering the high rate of repeat chlamydia test positivity following therapy, the *in vitro* data suggesting differences in azithromycin versus doxycycline anti-chlamydia activity, and clinical data suggesting chlamydia treatment failure in women denying post-therapy sexual activity, we conducted a single center, phase III randomized treatment trial of CDC-recommended azithromycin versus doxycycline regimens for chlamydia in males and females residing in long-term YCFs in Los Angeles County.¹⁶ Our study design was able to address major limitations of prior chlamydia treatment trials of azithromycin versus doxycycline. Of 567 participants enrolled December 2009 through April 2014, 284 were randomized to azithromycin and 283 to doxycycline. After accounting for early discontinuation before first follow-up at Day 28, 155 (55%) participants in each arm completed first follow-up and comprised the per protocol population (65% male and 35% female). The final study visit was completed May 2014. There were no treatment failures in the doxycycline arm. In the azithromycin arm, treatment failure occurred in five participants (3.2%; 95% CI: 0.4-7.4%). The observed failure rate difference in the treatments was 3.2%, with a 90% upper CI of 5.9%, exceeding the predetermined 5% cutoff for establishing azithromycin noninferiority. Treatment safety was also evaluated.

Gastrointestinal symptoms were the most common adverse events (AEs) in each treatment arm, reported in <10%. No severe or serious AEs occurred, and no participants were discontinued due to an AE.

The trial was not designed or powered to evaluate azithromycin efficacy in symptomatic chlamydia-infected males. However, in a subanalysis of 102 males receiving azithromycin, there was a higher frequency of treatment failure in those who reported painful urination compared with those who did not (2 of 20 [10.0%] vs. 2 of 82 [2.4%], $P=0.172$).¹⁶

2.2 Rationale

The proposed study is designed to determine the frequency of chlamydia treatment failure in males treated with azithromycin who do versus do not have urethral symptoms. Azithromycin is FDA approved for use in the U.S. and remains CDC recommended for urogenital chlamydia treatment (irrespective of urethral symptoms).⁴ As discussed above, a subanalysis from the

urogenital chlamydia treatment trial performed in YCFs suggested that the azithromycin treatment failure rate may be higher in males with urethral symptoms. Also, during the conduct of the trial, there were two nongonococcal urethritis (NGU) treatment trials that reported low azithromycin cure rates (77% and 86%) in men with symptomatic chlamydia urethritis.^{17,18} Taken together, these studies and the recent subanalysis suggest that azithromycin for treatment of chlamydia in males with urethral symptoms deserves further study.

Prior chlamydia treatment studies evaluating azithromycin had one or more major limitations: 1) not being able to exclude re-infection or new infection as an explanation for a repeat positive chlamydia test post-therapy; 2) not being able to ensure azithromycin is successfully re-dosed in those who vomit within one hour of azithromycin administration; and 3) not always confirming the chlamydial infection is present at the time the treatment is initiated (some infections may have already resolved when patients return for treatment of a positive screening chlamydia test). Our study addresses these limitations through: 1) use of a study population where repeat infection from an untreated partner is very unlikely (a gender-segregated YCF population where subjects are screened and treated for chlamydia upon entry into the facility); 2) repeating chlamydial testing at the time treatment is initiated to ensure chlamydial infection is still present; 3) performing *C. trachomatis* OmpA genotyping on chlamydia strains in those with repeat infections to exclude new infection (and to confirm treatment failure with the same strain); and 4) administration of azithromycin as directly observed therapy and then re-dosing the medication if vomiting occurs within one hour of initial administration. In addition to evaluating the azithromycin treatment failure rate in males based on presence of urethral symptoms, this study will also investigate whether the enrollment *C. trachomatis* OmpA genotype and median organism load are associated with treatment failure.

We hypothesize that the chlamydia treatment failure rate following azithromycin 1 gm administration will be significantly higher in males reporting urethral symptoms at the time of treatment. We also hypothesize that: 1) the enrollment OmpA genotype will not be associated with treatment failure, and 2) however a higher enrollment *C. trachomatis* organism load will be associated with a higher treatment failure rate.

Because study participant accrual rates at a single Los Angeles (LA) County YCF are too small to permit timely answers to the pressing question of frequency of chlamydia treatment failure in males following azithromycin administration, we propose to enroll at multiple YCFs in the LA County Correctional System, as was done for the prior clinical trial, to address our hypotheses. Facilities may be central detention centers, camps and/or placements that are part of the LA County YCF system.

2.3 Potential Risks and Benefits

2.3.1 Potential Risks

Azithromycin is FDA approved and is a first line recommended antibiotic for chlamydial infection treatment. In addition, azithromycin has been in use for many years with an excellent safety

profile. The major side effects are gastrointestinal, with nausea, vomiting, abdominal cramping, and diarrhea possible. On rare occasions, severe hypersensitivity allergic reactions to azithromycin, erythromycin, macrolide and ketolide drugs have been reported. Because azithromycin is principally eliminated via the liver, caution is recommended when azithromycin is administered to patients with impaired hepatic function (reference: package insert). We do not foresee any psychological, social, legal, economic, or any other risks to subjects.

2.3.2 Known Potential Benefits

Treatment of chlamydia may prevent complications in males (e.g., epididymitis and infertility) and transmission to others. This study may improve our understanding of the efficacy of azithromycin for treatment of uncomplicated urogenital chlamydia in males based on whether they have urethral symptoms. It may also provide insight into other factors influencing chlamydia treatment success.

3 OBJECTIVES

3.1 Study Objectives

- The primary objective of this study is to:

Assess the microbiological efficacy of azithromycin in uncomplicated *Chlamydia trachomatis* infection in males with versus without urethral symptoms in YCFs; in essence, this study will assess the frequency of chlamydia treatment failure to azithromycin at the Day 28 follow-up visit (Visit 2) in males with urethral symptoms compared to males without urethral symptoms.

- The secondary objectives of this study is to:

Evaluate the association of laboratory findings (enrollment chlamydia load and OmpA genotype) and other participant characteristics (demographics, sexual behaviors, etc.) to chlamydia treatment failure in males after azithromycin treatment.

3.2 Study Outcome Measures

3.2.1 Primary Outcome Measures

Day 28 Follow-up (Visit 2):

Microbiological Cure:

Aptima Combo 2® Assay (AC2) (Hologic, Inc., San Diego, CA, USA) is negative for *C. trachomatis* at the Day 28 follow-up visit (Visit 2).

Microbiological Failure:

AC2 is positive for *C. trachomatis* at the Day 28 follow-up visit (Visit 2) and *C. trachomatis* OmpA genotyping reveals the baseline chlamydial strain and the repeat positive chlamydial strain to have the same *ompA* sequence (i.e., concordant).

If a participant has discordant *ompA* sequences and no evidence for mixed strain infection, they will be classified as a new infection and not considered a microbiological failure.

OmpA genotyping is not successfully performed on the baseline or repeat positive chlamydial isolate (i.e., there is an insufficient number of *ompA* copies in the sample to successfully amplify), but the participant did not have an unsupervised furlough (i.e., a leave from the YCF) prior to the chlamydia testing and the participant denies sexual activity with another person in the interval between treatment and repeat testing.

Unevaluable:

Participant did not return for chlamydia testing at the Day 28 follow-up visit (Visit 2) or could not be tested for any reason at the Day 28 follow-up visit (Visit 2); this includes participants who are withdrawn from the study due to an AE or epididymitis.

Participant had an AC2 negative for *C. trachomatis* at the time treatment was initiated (enrollment visit).

Participant vomits the single dose of azithromycin within one hour of administration and is not successfully re-dosed with azithromycin within 24 hours of the initial treatment.

Participant did not complete therapy.

Participant has an unsupervised furlough.

Indeterminate Outcome:

C. trachomatis OmpA genotyping cannot be successfully performed on the repeat chlamydial isolate and the participant reports sexual exposure in the interval between treatment and repeat testing or the participant had an unsupervised furlough prior to the chlamydia test. These participants will be excluded from the primary analysis.

3.2.2 Secondary Outcome Measures

The study will evaluate whether demographical characteristics (collected at baseline) and clinical parameters (collected at baseline and follow-up visits) predict treatment outcome (treatment success versus failure). In addition to the more extensive STD clinical parameter assessment that occurs at baseline, clinical parameters will be recorded for all participants at each follow-up visit.

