7 STUDY SCHEDULE

Schedule of study visits:

Visit 1 – Enrollment

Visit 2 – Day 28 after study drug initiation

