8 STUDY PROCEDURES/EVALUATIONS

8.1 Clinical Evaluations

- Prior to enrollment, results and date of the screening chlamydia and gonorrhea test (part of juvenile intake procedure) will be obtained by study site personnel. Only those with a positive chlamydia test and negative gonorrhea test will be approached for possible enrollment.
- After consent is obtained, additional eligibility criteria will be determined. This includes assessing if participant has received antimicrobial therapy with activity against *C. trachomatis* within 21 days of positive chlamydia screening NAAT (or in the interval between the positive screening NAAT and study enrollment) and whether participant has epididymitis symptoms based on medical records. If a participant is noted to have received antimicrobial therapy with activity against *C. trachomatis* usage within 21 days of screening or has had a clinical diagnosis of epididymitis between screening and enrollment, then the participant is ineligible.
- Eligible participants will be enrolled and demographic information (race, ethnicity and date of birth), STD history, and sexual history will be recorded onto a data collection form at the enrollment visit.
- At the end of the enrollment visit, azithromycin 1 gm is administered to each participant and ingestion is directly observed and time of administration recorded.
- At the enrollment visit, counseling will be given regarding the importance of sexual abstinence during the course of the study.
- Prior to the follow-up visit, AC2 test results from the enrollment visit are reviewed to ensure continued eligibility.
- At follow-up visit, medical history including epididymitis symptoms, sexual history including sexual activity, information on furloughs, defined AEs (see Section 9.2.1), and SAEs are recorded. Results of AC2 testing at each visit are reviewed when they become available and are used for classification of treatment outcomes for that visit.

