11 STATISTICAL CONSIDERATIONS

11.1 Study Hypotheses

The primary objective of this study is to determine whether there is a significant difference in the urogenital chlamydia treatment failure rate in males treated with azithromycin 1 gm who do versus do not have urethral symptoms. We hypothesize that the chlamydia treatment failure rate will be significantly higher in males with urethral symptoms compared with no symptoms at the time of azithromycin treatment. The primary endpoint, treatment failure, will be evaluated at the Day 28 follow-up visit (Visit 2). As a secondary endpoint, treatment failure will be evaluated based on treatment outcome assessed at the Day 28 follow-up visit (Visit 2) and all non-study visits. Secondary objectives of the study are to determine whether the enrollment OmpA genotype and the enrollment *C. trachomatis* organism load are associated with treatment failure.

We hypothesize that OmpA genotype will not be associated with treatment failure, however there will be a significantly higher median *C. trachomatis* organism load in those with treatment failure compared to the median load in those without treatment failure.

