11.5 Final Analysis Plan

For each of the two groups of males (those with versus without urethral symptoms), the binomial proportion and its 95% confidence interval will be used to estimate the failure rate. The Mantel-Haenszel-Cochran test will be used to compare the two groups across YCFs with respect to failure rate. To evaluate racial and ethnic group variation with respect to failure rate, a logistic

regression analysis will be performed with failure rate as the outcome variable, and with symptom status (symptomatic, asymptomatic), race and ethnicity included as covariates. While the primary analysis will use the combined urethral symptom variable (discharge and/or dysuria), secondary analyses with each urethral symptom will also be performed.

An ordinal scale will be used to quantify the intensity of each AE (0-None, 1-Mild, 2-Moderate, and 3-Severe). The incidence and severity level of AEs will be summarized for all subjects for each visit.

To assess the association between clinical/laboratory parameters and chlamydia treatment failure, including OmpA genotype and *C. trachomatis* organism load, univariate analyses of each factor against treatment failure will be conducted using Fisher's exact test for dichotomous factors and the Wilcoxon rank sum test for continuous variables. Those which are statistically significant at the 0.10 level will be incorporated into a logistic regression model. Since the underlying treatment failure rate is expected to be 0.04 (approximately 13 of 357 evaluable subjects), it may be difficult to identify characteristics that are associated with failure rate.

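### Section 3.2.2 lets clinical parameters collected at Day 28 serve as predictors of an outcome determined at Day 28, and Section 11.5 sets no limit on when candidates were measured (minor; secondary analysis only)

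*Combined protocol and SAP*

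**What the plan says.** Section 3.2.2 sets out to evaluate whether "clinical parameters (collected at baseline and follow-up visits) predict treatment outcome (treatment success versus failure"). The same sentence places demographic characteristics at baseline only, and the section adds that clinical parameters are recorded for every participant at follow-up.

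Section 7 lists two visits: enrollment, and "Visit 2 – Day 28 after study drug initiation". Section 11.1 fixes the endpoint at that second visit: "The primary endpoint, treatment failure, will be evaluated at the Day 28 follow-up visit (Visit 2"). Section 8.1 classifies each visit's outcome from that visit's AC2 result. It names, among the items recorded at follow-up, "medical history including epididymitis symptoms, sexual history including sexual activity, information on furloughs", together with adverse events. Section 7.3 describes the Visit 2 assessment as covering the time since enrollment.

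Section 11.5 gives the analysis. "To assess the association between clinical/laboratory parameters and chlamydia treatment failure", each factor is tested singly by Fisher's exact test or the Wilcoxon rank sum test. Then: "Those which are statistically significant at the 0.10 level will be incorporated into a logistic regression model". No measurement time is stated. Sections 3.1 and 11.1 tie only organism load and OmpA genotype to enrollment.

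Section 3.2.1 uses one of the follow-up items in the outcome itself. Where genotyping does not succeed, a failure requires that there was no unsupervised furlough and that "the participant denies sexual activity with another person in the interval between treatment and repeat testing". If the repeat isolate cannot be genotyped and "the participant reports sexual exposure in the interval between treatment and repeat testing", the outcome is indeterminate and the participant leaves the primary analysis.

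**The concern.** A predictor of treatment failure should be known before the failure, or at least not be produced by it. A Visit 2 symptom is recorded after treatment and at the same visit as the test that defines failure. If infection has persisted, the symptom may be its result. Entered in a model of failure, it would carry an odds ratio that reads as prognostic when the direction may be the reverse.

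This is not an inference from silence: 3.2.2 expressly admits follow-up parameters, and 11.5 does not narrow the list. At stake is how the secondary predictor findings are interpreted. Interval sexual activity raises a second question, because it helps to decide who is called a failure.

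**Working it through.** **1. Timing, item by item**

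| Candidate | When fixed | Source | Affected? |
|---|---|---|---|
| Urethral symptoms (primary exposure) | Time of treatment | 11.1 | No |
| Organism load, OmpA genotype | Enrollment | 3.1, 11.1 | No |
| Demographics | Baseline | 3.2.2 | No |
| Clinical parameters | Baseline and follow-up | 3.2.2 | Yes, the follow-up part |

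Only the follow-up clinical parameters lack a time limit.

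**2. Which Visit 2 items can still vary among evaluable participants**

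- Unsupervised furlough makes a participant unevaluable (3.2.1), so only supervised furloughs can vary.
- Clinically diagnosed epididymitis leads to withdrawal (5.3.1) and an unevaluable outcome (3.2.1), so only undiagnosed symptoms remain.
- Interval sexual activity can vary, subject to the outcome rule in step 5.
- Other clinical findings since enrollment (7.3) can vary, but the protocol does not list them.

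**3. Expected failures**

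Inputs from 11.2: 72 symptomatic males with 10% failing, and 285 asymptomatic males with 2% failing.

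0.10 × 72 + 0.02 × 285 = 7.2 + 5.7 = 12.9, and 12.9 / 357 = 0.036.

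This agrees with the 0.04, or about 13 of 357, in 11.5. The screen would therefore compare about 13 failures with 357 − 13 = 344 cures.

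**4. Could a consequence of failure pass the 0.10 screen?**

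The documents give no frequencies, so those below are assumptions. The probability that a two-sided Fisher test gives p ≤ 0.10 is summed over all outcomes of Binomial(13, frequency in failures) and Binomial(344, frequency in cures).

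| Frequency in cures | Same in failures (no association) | 10% in failures | 20% | 30% | 50% |
|---|---|---|---|---|---|
| 2% | 0.028 | 0.379 | 0.765 | 0.935 | 0.998 |
| 5% | 0.045 | 0.178 | 0.546 | 0.822 | 0.990 |
| 10% | 0.048 | 0.048 | 0.286 | 0.608 | 0.958 |

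The 10%/10% cell is itself a no-association case. Entry is possible and, for a strong marker, likely; it is not assured. The table shows what the rule permits and does not estimate this trial's risk.

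**5. Does the outcome rule alone make interval sexual activity look predictive?**

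Let s be the share reporting interval activity, equal in true failures and cures. Let g be the share of failures that cannot be genotyped, independent of s. Active, ungenotyped failures are not classified as failures. The classified failures are then in proportion s(1 − g) active to (1 − s) inactive, and

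odds ratio = [s(1 − g)/(1 − s)] / [s/(1 − s)] = 1 − g.

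For assumed g of 5%, 10%, 20% and 30%, this is 0.95, 0.90, 0.80 and 0.70. The number of failures removed is 13 × s × g, from 13 × 0.02 × 0.05 = 0.013 to 13 × 0.10 × 0.30 = 0.39 persons.

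Putting the active share among classified failures, s(1 − g)/[s(1 − g) + 1 − s], through the screen of step 4 (still 13 and 344) gives probabilities of 0.015 to 0.042 over s of 2% to 10% and g of 5% to 30%. At each s this is below the no-association rate (0.028, 0.045 and 0.048 for s of 2%, 5% and 10%). The circularity exists in principle but has a negligible numerical effect.

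**The case against.** The strongest reply is that 3.1 and 11.5 speak of association, and a Day 28 correlate of failure is a legitimate association; the concern leans on one verb in 3.2.2. That is fair as far as it goes. But 3.2.2 does say predict, the trial's title refers to predictors, and 11.5 feeds all screened factors into one model of failure.

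A second reply also stands in part: measured at Visit 2 does not mean arising at Visit 2. Section 9.2.1 records the onset of gastrointestinal events, and 9.1 says that gastrointestinal tolerability could influence efficacy. An event soon after dosing precedes the outcome and need not be its consequence, so excluding everything collected at Visit 2 would go too far.

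A reader might also infer stronger points that the documents do not support:

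- That interval sexual activity would emerge as a spurious predictor because it is part of the outcome rule. Step 5 shows otherwise.
- That the scarcity of events is evidence of this defect. Thirteen events limit any covariate, whenever measured, and 11.5 already acknowledges the difficulty.
- That follow-up sexual history is taken only in failures, from the description in 15.3. Sections 3.2.2 and 8.1 and Appendix A collect it at Visit 2 without an outcome condition, so 15.3 is loose wording.
- That there is no baseline clinical assessment, because Appendix A marks the clinical-parameter row at Visit 2 only. The medical and sexual history rows are marked at Visit 1 and plausibly carry it.

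**Conclusion.** The point holds as a minor one, confined to the secondary predictor analysis. The plan expressly admits Day 28 clinical parameters as predictors of a Day 28 outcome and sets no timing condition on entry to the model, so a consequence of persistent infection could be reported as a predictor of azithromycin failure.

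Its size cannot be stated from the documents. The screening probabilities rest on assumed frequencies and show only that entry is possible. It would be wrong to infer that the primary result is compromised: the primary comparison uses symptoms at the time of treatment, and no sample size figure changes. The two laboratory predictors with stated hypotheses are fixed at enrollment and are also unaffected.

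**What to change.** In 3.2.2 and 11.5, limit candidate predictors in the failure model to variables measured at enrollment. If wanted, add gastrointestinal events with a recorded onset soon after dosing, with the onset window stated in advance. Report the other Visit 2 clinical parameters (symptoms, interval sexual activity, furloughs) descriptively, as correlates of outcome.

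As a wording point, align 15.3 with 3.2.2, 8.1 and Appendix A, so that it is clear that sexual history is taken at Visit 2 regardless of outcome.

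The cost is a few sentences in three sections. No visit, procedure, data item or participant is added, and no data are lost. The downside is that the remaining Visit 2 items are described, not modelled.
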